11.0 STATISTICAL ANALYSIS PLAN

11.1 Statistical Analysis Plan

11.1.1 Demographic and Baseline Characteristics

Patient demographic and baseline characteristics, including age, gender, medical history, and prior therapy, will be summarized using descriptive statistics. For continuous variables, descriptive statistics (number [n], mean, standard deviation, standard error, median (range) will be provided. For categorical variables, patient counts and percentages will be provided.

11.1.2 Toxicity Analysis

Observed toxicities will be summarized by type (organ affected or laboratory determination such as absolute neutrophil count), severity (by NCI CTCAE v4.03 and nadir or maximum values for lab measures), date of onset, duration, reversibility, and attribution.

11.1.3 Analysis of Anti-tumor Activity

This study will aim to obtain preliminary estimates of the anti-tumor activity of the study combination. ORR will be calculated as the proportion of evaluable patients that have confirmed CR or PR, as defined according to the 2014 Lugano Classification, exact 95% confidence intervals will be calculated for these estimates. Response rates will also be evaluated based on number and type of prior therapy(ies). Time to response, duration of response, as well as progression-free survival and overall survival will be estimated using the product-limit method of Kaplan and Meier.

These efficacy analyses will be performed separately for DLBCL, FL, and HL patients. Any patient treated at the RP2D, including those from the dose-escalation cohort, will be included in efficacy analyses. Patients will be evaluable for efficacy assessment if they received at least one dose of vorinostat and one dose of pembrolizumab and underwent at least one response assessment. Patients will be evaluable for efficacy if they discontinued study therapy prior to the first response assessment because of progression of disease rather than solely because of unacceptable toxicity, withdrawal of consent, or investigator decision. If a patient discontinues study treatment prior to the first response assessment due to progressive disease, the treating physician is encouraged to obtain imaging to confirm progression.

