ORR will be calculated as the proportion of evaluable patients that have confirmed CR or PR, as defined according to the 2014 Lugano Classification, exact 95% confidence intervals will be calculated for these estimates. CR rate will be similarly estimated. Response rates will also be evaluated based on number and type of prior therapy(ies). Duration and time to response (DOR and TTR), as well as overall survival (OS) and progression-free survival (PFS) will be estimated using the product-limit method of Kaplan and Meier.

Because of the unique immune-related adverse events (IrAEs) observed with checkpoint inhibitors, we will monitor for “unacceptable toxicity” with this new combination of drugs (defined in [Section 10.2](#)). The expected rate of “unacceptable toxicity” should not be $\geq 33\%$. The early stopping rule for unacceptable toxicity will be assessed after enrollment of 12 patients (total, across cohorts) treated at the RP2D and will be assessed once the 12th patient has completed at least 4 cycles of therapy. If >3 “unacceptable toxicity” events occur in the first 12 patients ($\geq 33\%$) treated (across disease subtypes) at RP2D, or at a rate $\geq 33\%$ thereafter at the quarterly review, accrual will be halted and a full review of these events will be performed by the City of Hope Data Safety Monitoring Committee (DSMC). Patient accrual will not resume until approved by the DSMC to do so. These rules are in addition to the quarterly review of all toxicities submitted to the City of Hope Data Safety Monitoring Committee (DSMC). Patients with ongoing toxicity will be followed until resolution or stability.

Sponsor/Licensee:

Investigator-initiated trial at City of Hope
Supported by Merck, Inc.

Case Report Forms

Medidata Rave EDC®

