7.4 Replacement of Subjects

During the Phase I dose escalation portion of the study, subjects will be replaced for any of the following:

- Missed 30% or more doses of vorinostat during the DLT period (not due to DLT).
- Did not receive the dose of pembrolizumab during the DLT period.
- Study drug discontinuation for any reason other than DLT during the DLT period.

Subjects who are replaced for missed doses may continue to receive study treatment if there is clear clinical benefit, but will not be included in DLT analysis.

During the expansion cohort portion of the study, subjects who discontinue study therapy prior to the first tumor response assessment for a reason other than progressive disease will be replaced.

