8.0 TRIAL FLOW CHART (STUDY CALENDAR)

8.1 Study Flow Chart

Trial Period:	Screening Phase	Treatment Cycles ^a												End of Treatment	Post-Treatment	
		To be repeated beyond 8 cycles				8				Discon	Safety Follow-up	Follow Up Visits ^g	Survival Follow-Up			
Treatment Cycle/Title:		1	2	3	4	5	6	7	8				D 1		D 15	
		D 1	D 8	D 15	D 1	D 1	D 1	D 1	D 15				D 1		D 15	
Scheduling Window (Days):	-28 to D1	± 3	± 3	± 3	± 3	± 3	See b	± 3	± 3	± 3	± 3	See b	At time of Discon ^l	30 days post discon ^m	Every 12 weeks post discon [†]	
Administrative Procedures																
Informed Consent	X															
Inclusion/Exclusion Criteria	X															
Demographics and Medical History	X															
Prior and Concomitant Medication Review	X															
Post-study anticancer therapy status													X	X	X	
Survival Status		X		X	X	X		X	X	X	X		X	X	X	X
Clinical Procedures/Assessments																
Vorinostat administration		X		X	X	X		X	X	X	X					
Pembrolizumab administration		X		X	X	X		X	X	X	X					
Review Adverse Events		X	X		X	X	X	X	X	X	X		X	X		
Physical Examination	X	X	X		X	X	X	X	X	X	X		X	X		
Vital Signs, Weight, and oxygen saturation	X	X	X		X	X	X	X	X	X	X		X	X		
ECOG Performance Status	X	X	X		X	X	X	X	X	X	X		X	X		
Buccal swab		X														
Laboratory Procedures/Assessments: analysis performed by LOCAL laboratory																

CONFIDENTIAL

Page 77 of 152

Trial Period:	Screening Phase	Treatment Cycles ^a												End of Treatment	Post-Treatment		
		1			2		3		4		To be repeated beyond 8 cycles				Discon	Safety Follow-up	Follow Up Visits ^g
Treatment Cycle/Title:		D 1	D 8	D 15	D 1	D 1	D 1	D 15	D 1	D 1	D 1	D 1	D 15				
		± 3	± 3	± 3	± 3	± 3	± 3	See b	± 3	± 3	± 3	± 3	See b	At time of Discon ^l	30 days post discon ^m	Every 12 weeks post discon [†]	
Pregnancy Test - Urine or Serum β-HCG ⁿ	X ^{**}	X			X	X	X		X	X	X	X		X	X		
PT/INR and aPTT [*]	X																
CBC with Differential [*]	X	X	X	X	X	X			X	X	X	X		X	X		
Comprehensive Serum Chemistry Panel ^c *	X	X	X	X	X	X			X	X	X	X		X	X		
Urinalysis [*]	X																
T3, FT4 and TSH (thyroid panel)		X			X				X					X			
12-lead ECG	X	X			X	X	X		X					X			
Efficacy Measurements																	
PET-CT or CT N/C/A/P ^e	X							X				X	X ^k		X ^d		
Tumor Biopsies/Archival Tissue Collection/Correlative Studies Blood																	
Archival or Newly Obtained Tumor Tissue Collection	X												X ^f				
Bone Marrow Aspirate and Biopsy ^j	X ⁱ																
Correlative Studies Blood Collection		X		X				X ⁱ				X ^h					

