9.1.5.3 Subsequent Anti-Cancer Therapy Status

The investigator or qualified designee will review all new anti-neoplastic therapy initiated after the last dose of trial treatment. If a subject initiates a new anti-cancer therapy within 30 days after the last dose of trial treatment, the 30 day Safety Follow-up visit must occur before the first dose of the new therapy. Once new anti-cancer therapy has been initiated the subject will move into survival follow-up.

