9.5.3.4 Follow-up Visits

Subjects who discontinue trial treatment for a reason other than disease progression will move into the Follow-Up Phase and should be assessed every 12 weeks (84 ± 7 days) by radiologic imaging to monitor disease status. After 1 year, the imaging time point will occur every 18 weeks (± 7 days). Every effort should be made to collect information regarding disease status until the start of new anti-neoplastic therapy, disease progression, death, and end of the study. Information regarding post-study anti-neoplastic treatment will be collected if new treatment is initiated.

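### ORR and CR rate can leave out RP2D patients who exit before any scan without PD, and DOR does not count death as an event

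*Combined protocol and SAP*

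**What the plan says.** **Denominator.** Section 11.1.3 states that "ORR will be calculated as the proportion of evaluable patients that have confirmed CR or PR". The synopsis adds, for complete response, that "CR rate will be similarly estimated". To be evaluable a patient needs at least one dose of each drug and at least one response assessment. A patient who stopped before the first assessment is evaluable if the stop came "because of progression of disease rather than solely because of unacceptable toxicity, withdrawal of consent, or investigator decision". The same section also says "Any patient treated at the RP2D, including those from the dose-escalation cohort, will be included in efficacy analyses", and Section 10.2 defines both rates over patients with no evaluability limit, counting responses documented during study treatment.

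**Replacement.** In the expansion cohort, Section 7.4 provides that "subjects who discontinue study therapy prior to the first tumor response assessment for a reason other than progressive disease will be replaced". Section 11.3 refers to 11.1.3 for expansion evaluability, plans 52 evaluable patients and caps accrual at 60 to allow for replacement.

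**Scans after stopping.** The follow-up column of the flow chart (Section 8.1) reads "Every 12 weeks post discon", and Section 9.5.3.4 says "Subjects who discontinue trial treatment for a reason other than disease progression will move into the Follow-Up Phase" for imaging. Section 9.1.5.3 limits this: "Once new anti-cancer therapy has been initiated the subject will move into survival follow-up".

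**DOR.** Section 10.2 runs DOR from first PR or CR to PD. Patients without progression are censored at last follow-up, or at the start of non-protocol lymphoma treatment. Death is not mentioned. The PFS definition in the same section does count death from any cause.

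**The concern.** Whether a patient enters the ORR and CR-rate denominator depends on what happens after treatment starts. Exits through toxicity, withdrawal of consent, investigator decision or death without PD may be linked to how the regimen is tolerated or how the patient is faring. Removing and replacing them gives a response rate among those who stayed long enough to be scanned, rather than among those treated. The direction is fixed: a patient with no assessment cannot be a responder.

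DOR has a parallel gap. A responder who dies without documented PD leaves the risk set as if still in remission, which can only lengthen the Kaplan-Meier estimate.

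No hypothesis test rests on these endpoints, but they are the plan's only estimates of anti-tumor activity. Section 4.6.4 cites an observed response count (13 of 15) as the reason to enrol 10 more patients, so response figures do inform decisions in this trial.

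**Working it through.** **1. The plan's own figures.** 12 + 40 = 52 evaluable (Section 11.3), which agrees with 42 + 10 = 52 (Section 4.6.4). Accrual headroom is 60 − 52 = 8, or 8/60 = 13.3%. It is shared with escalation patients replaced for DLT evaluability. There is no power calculation to reproduce.

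**2. Who can be lost.** With 21-day cycles, the first on-treatment scan (cycle 4, day 15–21, −3 days) falls on study day 63 + 15 − 3 = 75 to 63 + 21 = 84. That is a long window for a non-PD exit.

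- Clear losses: death without PD, full withdrawal of consent, or new anti-cancer therapy before any scan.
- Uncertain: a toxicity stop followed by an off-treatment scan. For a stop on day 22, counting 84 ± 7 days from discontinuation puts that scan on day 22 + 77 = 99 to 22 + 91 = 113. Footnote g of the flow chart instead counts from the last on-treatment scan, which this patient does not have. Section 11.1.3 does not say whether an off-treatment scan makes a patient evaluable, while 10.2 counts responses only during treatment.

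**3. Effect on the rates.** With r responders, n evaluable and x excluded exits:

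all-treated rate = r/(n + x) = (r/n) × n/(n + x)

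The cohort size (n = 20) and x are assumptions. The factors are 20/21 = 0.952, 20/22 = 0.909 and 20/24 = 0.833. The starting rates are those assumed in Section 11.4: about 30% CR in HL, and 40–50% response in DLBCL and FL. Exact 95% intervals are in brackets where computed.

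| Evaluable set | x = 1 | x = 2 | x = 4 |
|---|---|---|---|
| 6/20 = 30.0% (11.9–54.3) | 28.6% (11.3–52.2) | 27.3% (10.7–50.2) | 25.0% (9.8–46.7) |
| 8/20 = 40.0% (19.1–63.9) | 38.1% | 36.4% | 33.3% (15.6–55.3) |
| 10/20 = 50.0% (27.2–72.8) | 47.6% (25.7–70.2) | 45.5% (24.4–67.8) | 41.7% (22.1–63.4) |

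For the 10 added HL patients, an assumed 6/10 = 60.0% becomes 6/11 = 54.5% or 6/12 = 50.0%.

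As a pooled outer case, take 40 + 6 = 46 evaluable at the RP2D (Section 7.1.2 allows at most 6 evaluable per escalation level) and let all 8 headroom patients be early RP2D exits. The factor is 46/54 = 0.852. Then 23/46 = 50.0% (34.9–65.1) becomes 23/54 = 42.6% (29.2–56.8), and 14/46 = 30.4% (17.7–45.8) becomes 14/54 = 25.9% (15.0–39.7). With no exits there is no difference.

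**4. Effect on DOR.** The documents give no inputs. Assume exponential times, a PD-only median of 12 months, and yearly probability d of death without PD:

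median = ln 2 / [ln 2/12 − ln(1 − d)/12]

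For d = 5%, 10% and 15% the median is 11.2, 10.4 and 9.7 months, against 12.0 when deaths are censored.

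**The case against.** The plan also contains all-patient wording: Sections 4.6.5.2 and 10.2 define ORR over patients, and 11.1.3 says every RP2D patient is included in efficacy analyses. On that reading this is an inconsistency to reconcile, not a chosen bias. But the sentence that says how ORR is calculated names evaluable patients, two sentences then define them, and Sections 7.4 and 11.3 are built around that definition. The broader wording does not cancel this. At best the plan supports two denominators in an open-label trial with responses already seen.

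The excluded group is narrower than all early stops, and this stands. Early PD exits are kept as non-responders. Sections 7.6.1.2 and 7.7.1 allow one drug to continue when the other is stopped or held, so some toxicity cases still reach the cycle 4 scan. Others may be scanned in follow-up.

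The size is assumed, and the shifts lie well inside the exact intervals. That is true, but the intervals do not describe a shift that always goes one way. Four exits among 24 patients in one histology is a high share (16.7%), yet it fits within the study-wide allowance of 8.

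Nothing shows that the 13 of 15 count was inflated by this rule, and no such claim is made. Deaths left out of DOR are still events in PFS and OS, which limits the harm but does not correct DOR.

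Finally, changing the main denominator after responses are known has its own cost. This is why the fix keeps the planned rate in view and dates the change.

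**Conclusion.** The concern holds and should be fixed. Followed as written, the plan can only raise ORR and CR rate relative to all treated patients, and can only lengthen DOR. For 1 to 4 exits in an assumed cohort of 20 evaluable patients, the evaluable-set rate is multiplied by 0.952 to 0.833 to give the all-treated rate; the pooled outer case is 0.852. The DOR medians show direction and rough size only. The number of exits, the cohort sizes, the 6/10 responder count and all DOR inputs are assumptions. The 30% and 40–50% rates come from the exploratory correlative section, not from ORR planning. The direction depends on none of these, only on a fixed definition of a responder. The primary toxicity endpoint, sample size, alpha and power are unaffected.

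**What to change.** - **Sections 11.1.3 and 1.0:** make the main ORR and CR-rate denominator all patients who received at least one dose of study treatment at the RP2D, including those replaced under 7.4, and count patients with no assessment as non-responders. Report the evaluable-set rate beside it, labelled as such. State that the change was made after some responses had been seen.
- **Section 11.1.3:** state whether an off-treatment follow-up scan makes a patient evaluable, and align this with the on-treatment limit in 10.2.
- **Section 10.2:** define the DOR event as the earlier of PD and death from any cause.
- **Minor:** state that PFS and OS use all patients treated at the RP2D. Use one term, *documented* or *confirmed*, for response in 10.2 and 11.1.3. If *confirmed* is kept, define it for PR, since only CR confirmation is specified (Sections 9.2.6 and 10.1).

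The cost is protocol and SAP wording, with no new visits or data. The estimates may be slightly less favourable, and counting early withdrawals as non-responders is conservative. Because 42 patients had been enrolled with responses observed (Section 4.6.4), this is a post-data change, so both rates and the timing need to be reported.

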11.2 Safety Analysis and Stopping Rules for Excessive Toxicity in the Expansion Cohort

During enrollment into the expansion cohort, toxicity information recorded will include the type, severity, and the probable association with the study regimen. Tables will be constructed to summarize the observed incidence by severity and type of toxicity.

Because of the unique immune-related adverse events (IrAEs) observed with checkpoint inhibitors, we will monitor for “unacceptable toxicity” with this new combination of drugs

(defined in [Section 10.2](#)). The expected rate of “unacceptable toxicity” should not be $\geq 33\%$. The early stopping rule for unacceptable toxicity will be assessed after enrollment of 12 patients (total, across cohorts) treated at the RP2D and will be assessed once the 12th patient has completed at least 4 cycles of therapy. If >3 “unacceptable toxicity” events occur in the first 12 patients ($\geq 33\%$) treated (across disease subtypes) at RP2D, or at a rate $\geq 33\%$ anytime thereafter at the quarterly review, accrual will be halted and a full review of these events will be performed by the City of Hope Data Safety Monitoring Committee (DSMC). Patient accrual will not resume until approved by the DSMC to do so. These rules are in addition to the quarterly review of all toxicities submitted to the City of Hope Data Safety Monitoring Committee (DSMC). Patients with ongoing toxicity will be followed until resolution or stability.

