7.1.1 Treatment Duration

Study treatment will continue until the subject completes 24 months of treatment with the study regimen, or experiences radiographically-confirmed PD (Section 9.2.6 and Section 9.2.6.1), unacceptable adverse experiences, either DLT (Section 7.2) or other unacceptable toxicity (section 10.2), or meets other criteria for study withdrawal or treatment discontinuation

7.1.2 Rules for Phase I Dose Escalation, De-Escalation and Expansion: Adapted Rolling 6 Design

This phase I trial will employ a modified Rolling 6 design, a more conservative version of the Rolling 6 design of Skolnik, et al²⁹. In this design, at most, 3 patients will be under observation for DLT on the current test dose level at any time. Patients who are not evaluable for DLT will be replaced. Once each patient is evaluable for toxicity and passes without a DLT, an additional patient *may* be accrued on that dose level – up to 6 patients. Once 3 patients are evaluable with no patient at that dose level experiencing a DLT, the dose can be escalated, or up to 3 additional patients may be treated at the current dose level. Although this design does not require that 6 patients be treated, no more than 6 evaluable patients will be accrued to any dose level during the dose finding portion of this study. If at any time, the dose level has 1 documented DLT with fewer than 6 evaluable patients, accrual will continue until 6 patients are evaluable. Escalation will terminate as soon as two or more patients experience any DLT attributable to the study treatment, at a given dose level. MTD will be declared at the highest dose level at which 6 patients have been treated and at most 1/6 patients experiences DLT. If more than 1/6 patients experiences DLT, then the next lower dose will be expanded. There will be no intrapatient dose escalation. These rules are outlined in Table 4:

Table 4. Dose Escalation Rules

# Patients on Current Level			Action
With DLT [^]	Evaluable	Evaluable + At Risk [^]	
0	0	1-2	Accrue next patient at this level*
0	0	3	Hold accrual
0	1	1-3	Accrue next patient at this level
0	1	4	Hold accrual
0	2	2-4	Accrue next patient at this level
0	2	5	Hold accrual
0	3-6	3-6	Accrue next patient at the next higher level* ^{+,+}
1	1	1-2	Accrue next patient at this level
1	1	3	Hold Accrual
1	2	2	Accrue next patient at this level
1	2	3-4	Hold accrual
1	3-5	3-5	Accrue next patient at this level
1	3-5	6	Hold accrual
1	6	6	Accrue next patient at the next higher level*

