7.5 Expansion Cohort

Once the RP2D has been determined, an expansion cohort of 40 patients will be enrolled and treated at the RP2D, to acquire additional safety and tolerability data about the combination. Toxicity monitoring will continue during the expansion segment. In addition, because of the unique immune-related adverse events (IrAEs) observed with checkpoint inhibitors, we will monitor for “unacceptable toxicity” with this new combination of drugs (defined in [Section10.2](#)). If >3 “unacceptable toxicity” events occur in the first 12 patients ($\geq 33\%$) treated (across disease subtypes) at RP2D, or at a rate $\geq 33\%$ thereafter at the quarterly review, we will halt accrual to fully evaluate these events and assess whether the regimen should be modified.

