10.2 Endpoint Definitions

Overall Response Rate (ORR): Defined as the proportion of patients that have a documented CR or PR at any time during study treatment.

Complete Response (CR) rate: Defined as the proportion of patients that have a documented CR at any time during study treatment.

Duration of Response (DOR): Defined as the time from the first achievement of PR or CR to time of PD. Patients who never achieve PR or CR are excluded. Patient who has not had disease progression/relapse at last follow-up is censored at the time of last follow-up. If a patient receives non-protocol anti-lymphoma treatment prior to disease progression, the patient is censored at the time of non-protocol anti-lymphoma treatment.

Overall Survival: Defined as time from initiation of study therapy to death from any cause. If a patient is alive at the last evaluation time period, survival time is censored at the time of last follow-up.

Progression-Free Survival (PFS): Defined as the time from initiation of study therapy to the first observation of disease relapse/progression or death from any cause, whichever occurs first. If the patient has not progressed relapsed or died, the patient is censored at the time of last follow-up. If a patient receives non-protocol anti-lymphoma treatment prior to disease progression, the patient is censored at the time of non-protocol anti-lymphoma treatment.

Toxicity: Toxicity and adverse events will be recorded using the NCI CTCAE 4.03 scale. Observed toxicities will be summarized by type (organ affected or laboratory determination such as absolute neutrophil count), severity (by NCI CTCAE v4.03 and nadir or maximum values for lab measures), date of onset, duration, reversibility, and attribution.

Unacceptable Toxicity: defined as one of the following AEs that is at least possibly related to study treatment, at any point on study therapy:

- Any Gr 3 or higher IrAE that does not resolve to Gr ≤ 1 within 7 days with the exception of:
 - Grade 3 immune-related hepatitis if ALT or AST $< 8 \times$ ULN or total bilirubin $< 5 \times$ ULN.
 - Grade 3 asymptomatic endocrinopathy.
 - Local inflammatory response to study therapy.
- Any other Gr ≥ 4 AE with the exception of:
 - Non-clinically significant laboratory abnormalities
 - Local inflammatory response to study therapy.
- Any Gr 5 AE.

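### The first-12 toxicity check in Sections 1.0 and 11.2 waits for the 12th patient to complete 4 cycles, has no fallback, and conflicts with Section 7.5 on when accrual halts

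*Combined protocol and SAP*

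**What the plan says.** - **Section 11.2** has two numeric limbs. Accrual halts if more than 3 unacceptable-toxicity "events occur in the first 12 patients" treated at the RP2D, or if the rate is 33% or more "anytime thereafter at the quarterly review". The DSMC then reviews the events, and accrual restarts only with its approval. On timing, the rule "will be assessed once the 12th patient has completed at least 4 cycles of therapy". Section 1.0 carries the same timing sentence.
- **Section 7.5** repeats both limbs with no 4-cycle condition: if either is met, "we will halt accrual to fully evaluate these events and assess whether the regimen should be modified".
- **Section 10.2** counts unacceptable toxicity "at any point on study therapy". Sections 7.1.1 and 7.12 make it a reason to stop treatment.
- **Section 7.4** says that in the expansion cohort "subjects who discontinue study therapy prior to the first tumor response assessment for a reason other than progressive disease will be replaced". The Section 8.1 footnotes place the first scan in cycle 4, days 15 to 21.
- **Oversight in parallel:** the DSMC reviews toxicity quarterly (11.2) and the Protocol Management Team (PMT) meets at least monthly (13.4). Neither review has a numeric threshold of its own before the first-12 look.

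**The concern.** The timing sentence hangs the look on one patient reaching a milestone, and this causes two problems.

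First, the milestone may never be reached. If the 12th patient progresses, withdraws or stops for toxicity before the end of cycle 4, the condition as written is not met, and no other date is given. The monitored event can itself prevent the look, since an unacceptable toxicity in the 12th patient is grounds for stopping treatment.

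Second, the first limb cannot be uncrossed. Once more than 3 events have occurred among the first 12, no later data can bring the count back down. Section 11.2 read literally still waits until 12 patients have been enrolled and the last has had 4 cycles, with enrolment open. Section 7.5 can be read as halting at once. A study team could follow either section and be in compliance, yet stop accrual months apart. The dose-escalation rule in Section 7.1.2 is not ambiguous in this way: "Escalation will terminate as soon as two or more patients experience any DLT attributable to the study treatment, at a given dose level".

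**Working it through.** **Inputs.** Boundary of more than 3 in 12 (11.2); 21-day cycles (2.1), so 4 cycles take 84 days; 52 expected and 60 maximum patients (11.3); 48 months of enrolment (1.0). The plan gives no monthly accrual rate, no onset-time distribution and no operating characteristics for the rule.

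**1. The plan's own figure.** 4/12 = 33.3%, which is at least 33%; 3/12 = 25%, which is not. The boundary agrees with its stated percentage.

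**2. How early the boundary is met.** Take one event per affected patient and a true rate p. Crossing has probability P(X ≥ 4), X ~ Binomial(12, p). The fourth affected patient is the k-th enrolled with probability C(k−1, 3) p⁴ (1−p)^(k−4).

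| p | P(cross) | fourth affected is among first 11, given crossing | mean position of fourth affected, given crossing |
|---|---|---|---|
| 0.20 | 0.205 | 78% | 9.65 |
| 0.33 | 0.597 | 87% | 8.88 |
| 0.40 | 0.775 | 91% | 8.35 |
| 0.50 | 0.927 | 96% | 7.48 |

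When the boundary is crossed, the fourth affected patient is usually enrolled before the 12th.

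**3. The fixed wait.** Implied accrual is 52/48 = 1.08 to 60/48 = 1.25 per month. 84 days / 30.4375 = 2.76 months. 2.76 × 1.08 = 3.0 and 2.76 × 1.25 = 3.4 patients enrolled between the 12th patient's start and the look.

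**4. Total excess when the boundary is crossed.** Simulation of 40,000 trials per setting, with Poisson accrual, onset assumed uniform over each affected patient's first 84 days, and the look 84 days after the 12th start. The excess runs from the fourth event to the look.

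| p | accrual per month | mean months | mean patients enrolled |
|---|---|---|---|
| 0.33 | 1.08 | 4.2 | 4.6 |
| 0.33 | 1.25 | 3.8 | 4.8 |
| 0.50 | 1.08 | 5.6 | 6.0 |
| 0.50 | 1.25 | 5.0 | 6.2 |

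At an assumed 2 to 3 patients per month and p = 0.33, the figures are 2.8 to 2.3 months and 5.7 to 6.9 patients. The model does not condition on the RP2D having already met the limit of 1 DLT in 6 patients that is needed to declare the MTD (7.1.2), so these averages are illustrative.

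**5. Whether the quarterly limb fills the gap.** Suppose it did apply before the look, with the rate taken as events over all treated at the RP2D. Four events among 13 patients is 30.8%, and among 15 is 26.7%. Both are below 33%, although the first-12 boundary has been crossed.

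**6. Effect of halting at the crossing.** If the count closes at the same look date, the same trials cross. The boundary stays at 4/12 and P(cross) stays at 0.597 for p = 0.33. Only the date of the halt changes.

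**The case against.** The strongest reply is that Section 11.2 need not be read literally. Its halt sentence is conditional on the events occurring, the 4-cycle sentence may only date the formal assessment, and Section 7.5 has no such condition. The PMT meets monthly with stopping rules on its agenda and could act. This stands to the extent that the documents do not settle the question. A reader might infer that the plan definitely fails to act on a fourth event. Section 7.5 does not support that; the defect is that 7.5 conflicts with 1.0 and 11.2.

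Three other strong readings also fail:

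- **That this is the trial's only numeric toxicity halt.** Section 7.1.2 ends escalation at two DLTs on a level, and 11.2 has the quarterly limb. What can be said is that no other numeric halt clearly applies to the RP2D expansion before the first-12 look. The word that opens the quarterly limb could mean after the 12th patient rather than after the look, but step 5 shows that this would not replace the first limb.
- **That a crossing at 4 of 6 patients is the typical size.** Six more patients at 1.25 to 1.08 per month take 4.8 to 5.5 months. Adding 2.76 gives 7.6 to 8.3 months and about 9 patients. The arithmetic is right but the case is extreme. The first 12 include escalation patients at that dose, and the MTD, which is the default RP2D, requires 6 treated with at most 1 DLT. Most of the four events would have to arise after day 42 or fall under the DLT exceptions.
- **That replacement under Section 7.4 moves the 12th patient.** Section 11.2 counts patients treated, and a replaced patient has been treated. A confirming sentence is useful, but the text does not redefine the count.

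Finally, Section 4.6.4 reports 42 patients enrolled, with 10 to follow. On the planned 12 in escalation, that leaves 42 − 12 = 30 in the expansion, so the first look has probably passed. This limits the effect on future patients. It does not cure the rule as written, and it raises the question of which reading was applied.

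**Conclusion.** The point holds as a conflict and a gap in the timing of the rule. Sections 1.0 and 11.2 make the first-12 assessment depend on one patient completing 4 cycles, with no fallback and no accrual pause. Section 7.5 omits that condition. On the literal reading of 11.2, accrual can continue after a crossing that cannot be reversed.

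The firmest figure is about 3 extra patients during the 84-day wait, which needs only the accrual rate implied by the plan. The mean of about 4 months and 4.6 to 4.8 patients at a true rate of 0.33 also rests on the assumed onset within 84 days, one event per affected patient, and no allowance for the earlier DLT limit. The documents give no basis for the probability that the 12th patient stops early, so none is attached. The change is worth making because it is cheap and leaves the boundary alone, although its prospective effect is limited this late in enrolment.

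**What to change.** Reconcile Sections 1.0, 7.5 and 11.2 with one common text:

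- Accrual is halted for DSMC review as soon as the existing boundary of more than 3 is crossed among the first 12 patients treated at the RP2D.
- Otherwise the rule is assessed 12 weeks after the 12th treated patient's first dose, whether or not that patient is still on therapy. The quarterly limb applies from then on.
- The unit counted is stated. If it stays as events, nothing changes. If it becomes patients, say so openly: four events in three patients would halt accrual now and would not under a patient count.
- Patients replaced under Section 7.4 stay in the first 12 treated and in the quarterly denominator.

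Because 42 patients are already enrolled, also record when the first-12 rule was applied, on which patients, and with what count.

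The cost is a few sentences and one file note. Events are already collected each cycle. With the unit unchanged and the count closed at the same look date, the new text adds no halts and loses none.
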